#### **6.4.3.3 Safety**

N/A.

#### **6.4.3.4 Analysis of Subject Characteristics**

We will report baseline descriptive statistics for the overall study, by site, and for both the control and treatment arms of the study. These will include patient age, sex, race, ethnicity and all co-morbidities, medical history and clinical characteristics specified in Section 6.4.4 (**Appendix 6**). Baseline data will be compared using Pearson Chi Squared tests or Fisher exact test for dichotomous and/or categorical variables and student's t-tests for continuous variables. If variables are deemed as non-parametric, we will use a median test such as a Mann–Whitney *U*-test, where appropriate.

#### **6.4.3.5 Interim Analysis (if applicable)**

N/A

#### **6.4.3.6 Health economic evaluation**

N/A

#### **6.4.3.7 Other**

N/A

#### **6.4.4 Subsets and Covariates**

Covariates will include socio-demographic, socio-economic variables and clinical comorbidities such as age, sex, ethnicity, marital status, working status, level of education, weight, height and BMI (through patient self-report). Patients will also self-report if they have any of the following co-morbidities: hypertension, diabetes mellitus, high cholesterol, smoking history, alcohol use, sleep apnea, coronary artery disease (including myocardial infarction/heart attack), cancer, PTSD, or generalized anxiety disorder.

#### **6.4.5 Handling of Missing Data**

If patients are missing outcome data, we will use the last observation carried forward for the patient-reported outcome. Missing covariates will be set to missing.

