### 6.3.3 Screening

Patients will be identified by the sleep clinic coordinator and/or the sleep physician after their initial consult. Eligible patients must be aged between 22-64 years, English speaking, and have a diagnosis of chronic insomnia (see inclusion/exclusion criteria above in section 5.3.2). If they are interested clinic staff will notify the RA. Additionally, the patient will be provided with the study team's contact information if they wish to follow up. Eligibility will be determined by the sleep physician or coordinator stating that the patient is being seen for insomnia. The RAs will approach the patient for consent into the study while they are waiting for their sleep consult appointment/referral to see the sleep specialist. The wait time between enrollment and follow

up with sleep specialist is up to 12 weeks; therefore, this is a prime opportunity for patient enrollment and completion of this project.

The RA will also reach out to patients on the waitlist for in-person CBT-I upon the sleep clinician's approval. If the patient is interested in the study, the RA will attempt to arrange an in-person visit to conduct the consent and enrollment process. If an in-person visit is not possible, the RA will arrange a time for a Zoom call with the patient.

Additionally, a flyer will be circulated to the Sleep Clinic staff to provide to any patients who may express interest in the study (Appendix 7).

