Upon consent into the study, the patients will receive a Fitbit. For both arms of the study, Hugo will be used as a data collection platform as it aggregates data from multiple real-world data sources, thereby enabling the assessment of patient-reported outcomes, clinical outcomes, and healthcare utilization metrics. All participants will receive materials on sleep hygiene and healthy sleep tips. These sleep hygiene recommendations and healthy sleeping tips include behavioral information regarding getting a good night's sleep (e.g. setting a regular bed-time, getting out of bed if remaining awake, exercising regularly, not smoking). A full list of these tips can be found in **Appendix 1**. Patients will also receive a informational wallet card with study contact information (Appendix 8). Participants randomized to PEAR-003b will receive access to the therapeutic for 9

weeks a in addition to the sleep hygiene material. Post assessment data will be collected post intervention via diaries and questionnaires as outlined in the “Follow-up” section.

Because the Hugo platform obtains patient data through patient portals, all patients who connect will need a YNHH MyChart account. If the patient does not yet have a MyChart account, the RA will assist the patient in creating one. The RA will then assist the patient in linking their YNHH electronic health records to the Hugo platform as well as other health systems where they have received care by showing the study participant how to enter their patient portal credentials, provided that these health systems are connected to the Hugo platform.

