### 6.4.3 Planned Analysis

#### 6.4.3.1 Primary Analyses

For the primary endpoint analysis, we will use a  $t$  test to compare the ISI scores for the intervention (PDT + Fitbit) and control group (Fitbit only) at baseline (as this score is a continuous variable). We will then use a 2 (group)  $\times$  2 (time) repeated measures analysis of variance (RM ANOVAs) to compare pre to post changes from baseline to 9-weeks across groups. Paired sample  $t$  tests by group will be used to examine time effects within each condition (if the overall interaction effect is significant). At weeks 21, 35, and 61 post randomization we will also perform the same analysis, but this will be as an exploratory secondary endpoint. If a patient drops out, we will carry forward the most recent patient-reported outcome measure response. As this is an RCT, we expect that confounding will be minimal. If patients are missing outcome data, we will use the last observation carried forward for the patient-reported outcome. Missing covariates will be set to missing.

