#### 6.4.3.2 Secondary Objectives Analyses

For the secondary endpoint analysis regarding the patient reported outcomes, we will calculate the change in the PHQ-8, ESS, SF-12, PSS-10^22 and the GAD-7 scores at baseline and at 9-weeks, 21-weeks, 35-weeks and 61-weeks post randomization (as these are continuous variables) and perform a comparison between patients randomized to the intervention (PDT + Fitbit) and patients randomized to the control (Fitbit only). Based on our prior work using SHUTi, we will examine the change in scores between groups using a mixed model repeated measures ANOVA with an unstructured matrix, and estimated degrees of freedom (df) with Satterthwaite's correction. We will present df alongside F-test statistics and t statistics.

For the secondary clinical/healthcare utilization outcomes we will compare the PDT to the control at all follow-up time points. These outcomes will be defined as: (a) number of outpatient visits per patient with primary care physicians, (b) number of outpatient visits per patient with specialty care, (c) number of medication refills for sleep per patient, and (d) number of medication refills for psychotropic medications per patient. These comparisons will be examined using *t* tests at each time point (as these will be continuous variables).

For the sleep outcomes, we will calculate the change in each sleep outcome from baseline to 9-weeks, 21-weeks, 35-weeks, and 61-weeks post randomization comparing PDT to the control based on sleep diaries. These outcomes will be defined as: (a) sleep efficiency; (2) sleep onset latency [SOL], (3) number of awakenings, (4) sleep quality, and (5) total sleep time (minutes) (6) waking after sleep onset [WASO], (7) time in bed. We will examine the change in scores between groups using a mixed model repeated measures ANOVA. Paired-sample *t* tests will be used to examine time effects within each condition if the overall interaction effect is significant.

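### Unrestricted carry-forward of missing patient-reported outcomes conflicts with the planned mixed model and can bias the week 21, 35 and 61 comparisons in either direction

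*Combined protocol and SAP*

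**What the plan says.** Section 6.4.5, the general missing-data section, reads: "If patients are missing outcome data, we will use the last observation carried forward for the patient-reported outcome". Section 6.4.3.1 contains the same sentence and adds, for patients who leave: "If a patient drops out, we will carry forward the most recent patient-reported outcome measure response". The carried score may therefore come from baseline, week 9, week 21 or week 35.

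For PHQ-8, ESS, SF-12, PSS-10 and GAD-7, Section 6.4.3.2 says "we will examine the change in scores between groups using a mixed model repeated measures ANOVA", specified "with an unstructured matrix, and estimated degrees of freedom (df) with" a Satterthwaite correction. Diary outcomes also get a mixed model, with no covariance structure stated.

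ISI at the later visits is handled differently. Section 6.4.3.1 says "At weeks 21, 35, and 61 post randomization we will also perform the same analysis", meaning the 2 × 2 repeated measures ANOVA used at week 9, and calls this an exploratory secondary endpoint. Section 5.2.2 lists these ISI changes among the secondary outcomes.

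The plan does not say whether the mixed model is fitted to observed or to filled data. It plans no sensitivity analysis for missing data.

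**The concern.** The two instructions do not fit together. A likelihood-based mixed model with unstructured covariance needs no filling-in: each patient contributes the visits that were observed, and the estimates are valid if drop-out depends on observed scores. If missing visits are first filled by carry-forward, the model takes copied values as real measurements and that protection is lost. For ISI at weeks 21, 35 and 61 nothing has to be inferred, because the section that repeats the ANOVA at those visits also imposes carry-forward.

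At stake are the comparisons that show whether any benefit lasts. Access to the therapeutic runs for nine weeks from randomization (Section 6.3.4), and the last assessment comes 52 weeks after that. A patient last seen at week 9 would supply an end-of-treatment score as the week 21, 35 and 61 result. A patient who left before week 9 would supply a baseline score.

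**Working it through.** **Inputs from the plan.** 100 patients, 1:1 (Sections 6.1.3 and 6.4.2), so 50 per arm. Drop-out is given as 10%, with an effective N of 80 (Section 6.4.2). These disagree: 100 × (1 − 0.10) = 90, and 80 implies 20%. I use 10% to 20%. The plan's d = 0.52 serves below only as an assumed week-9 difference. It is not reproduced for a plain two-arm comparison at N = 80, two-sided 0.05 and 90% power: (1.960 + 1.282) × √(4/80) = 0.725. That is a separate matter and does not decide this point.

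**Assumptions.** The plan gives no ISI standard deviation, later course or timing of drop-out, so everything below is conditional.

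**Step 1: direction.** Let D9 and D61 be the true differences in favour of the therapeutic at weeks 9 and 61, p the drop-out proportion (equal in both arms and unrelated to outcome), and q the share of drop-outs who leave before week 9. Early leavers carry baseline (difference 0). As a simplification, all others carry week 9. Then

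bias at week 61 = p × [(1 − q) × D9 − D61].

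Carry-forward overstates the benefit only if D61 < (1 − q) × D9. Illustration in ISI points, with D9 = 5:

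| Course | p | q = 0 | q = 0.5 | q = 1 |
|---|---|---|---|---|
| Fades or controls catch up, D61 = 2 | 10% | +0.30 | +0.05 | −0.20 |
| | 20% | +0.60 | +0.10 | −0.40 |
| Maintained, D61 = 5 | 10% | 0 | −0.25 | −0.50 |
| | 20% | 0 | −0.50 | −1.00 |
| Grows, D61 = 7 | 10% | −0.20 | −0.45 | −0.70 |
| | 20% | −0.40 | −0.90 | −1.40 |

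For example, the first row at q = 0.5 is 0.10 × (0.5 × 5 − 2) = +0.05. The sign changes with the course and with the timing of drop-out.

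**Step 2: size in the case most favourable to overstatement.** Let the difference fall linearly from 0.52 SD at week 9 to 0 at week 61. At week 21 it is 0.52 × 40/52 = 0.40 and at week 35 it is 0.52 × 26/52 = 0.26. If drop-outs are spread evenly over the three intervals after week 9, the mean carried difference is (0.52 + 0.40 + 0.26)/3 = 0.39. The bias is 0.10 × 0.39 = 0.04 SD, or 0.20 × 0.39 = 0.08 SD. Adding an equally likely interval before week 9 gives (0 + 0.52 + 0.40 + 0.26)/4 = 0.295, hence 0.03 and 0.06 SD. If instead the 0.52 is maintained, with the same four intervals, the bias is −0.25 × 0.52 × p, that is −0.01 and −0.03 SD.

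**Step 3: effect on the test.** With a correlation of 0.5 between visits, the change score has SD √(2 × (1 − 0.5)) = 1, and the standard error of the difference is √(2/50) = 0.20. Biases of 0.04 and 0.08 SD give noncentralities of 0.2 and 0.4. With 98 df, the nominal 5% error rate becomes about 5.5% and 6.8%.

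**Step 4: would the planned model do better?** Simulation: 50 per arm, five visits, ISI SD 5, AR(1) correlation 0.6, baseline mean 18, monotone drop-out depending on observed scores, 2,000 runs. Week-61 estimates at 10% / 20% drop-out:

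| Course | Truth | Carry-forward | Likelihood, observed data |
|---|---|---|---|
| Therapeutic fades | 2.0 | 2.09 / 2.20 | 1.99 / 2.01 |
| Controls catch up | 2.0 | 2.06 / 2.11 | 1.99 / 1.96 |
| Maintained | 5.0 | 4.89 / 4.70 | 5.02 / 4.96 |
| Grows | 7.0 | 6.73 / 6.45 | 7.03 / 7.05 |

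Carry-forward errs in both directions, by up to 7.0 − 6.45 = 0.55 points. The likelihood estimate stays within 0.05 of the truth. The drop-out simulated here is of the kind the likelihood model handles. Relapse that itself causes drop-out is not covered by this check.

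**The case against.** A reader might infer that carry-forward will overstate durability: access ends at week 9, so later relapse among leavers is hidden, and controls who improve later are frozen at their week-9 score. The documents do not support that as a general statement. It requires the effect to fade, or controls to catch up, and most drop-out to follow week 9. Section 6.4.2 counts drop-out from baseline onward, and early leavers carry baseline, which shrinks the difference. Section 2.2 presents CBT-I as having lasting benefit, and under a maintained or growing effect the bias is zero or negative.

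The control-arm argument is also weaker than it looks. Section 6.3.3 says "The RA will also reach out to patients on the waitlist for in-person CBT-I", but Section 6.1.6 bars other non-medication insomnia programs during the study. The specialist wait is at most 12 weeks from enrollment. Randomization comes at about day 14, so week 9 falls about 11 weeks after enrollment; if waits are spread over that window, most specialist visits precede the week-9 assessment. Sleep medication remains allowed, so later improvement in controls is possible but not established.

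Two further objections carry weight. The plan does not expressly say that filling precedes the mixed model; that is the literal reading of an unqualified rule. The bias at the planned drop-out is also small, and it touches secondary endpoints only. None of this removes the conflict. A bias whose sign is unknown cannot be defended as conservative.

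**Conclusion.** The point stands as a direction-neutral one. Carry-forward for patient-reported outcomes is unrestricted, it is imposed on ISI at weeks 21, 35 and 61, and it is incompatible with the purpose of the mixed model planned for the other five instruments. For those five the defect is an unresolved conflict whose plain reading is filling. For later ISI it is explicit.

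Size: about 0.04 to 0.08 SD of false benefit at 10% to 20% drop-out if the whole effect vanishes by week 61 and all drop-out follows week 9, with the error rate rising from 5% to roughly 5.5% to 7%. The bias is smaller, or reversed, if some patients leave early or the effect lasts. These figures rest on assumed courses, correlations and timing, and on equal drop-out in the two arms. Diary outcomes are affected only if they count as patient-reported outcomes, which the plan does not settle. The week-9 primary analysis lies outside this point. The change should be made because it is cheap and the better method is already in the plan.

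**What to change.** In Section 6.4.5, state that carry-forward is not applied to outcomes analysed by mixed model. Then:

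- Fit the unstructured model of Section 6.4.3.2 to observed data for PHQ-8, ESS, SF-12, PSS-10 and GAD-7.
- In Section 6.4.3.1, use the same model on observed data for ISI at weeks 21, 35 and 61, in place of separate carried-forward 2 × 2 ANOVAs.
- State that diary outcomes are likewise analysed on observed data in their planned mixed model.
- Keep carry-forward only as a labelled sensitivity analysis, ideally beside a simple missing-not-at-random analysis, since a likelihood model does not deal with relapse that itself causes drop-out.

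The cost is SAP wording and a little extra programming. No new data are needed, and the main model is already planned.

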## 7 Trial Administration

### 7.1 Ethical Considerations: Informed Consent/Accent and HIPAA Authorization

**Compensation:** Patients will receive a stipend for their time contributed as part of this study. Estimated hourly stipend based on the average minimum wage in Connecticut and Minnesota (\$10) will be provided. This stipend will cover the consent process, initial set up and baseline questionnaire (3 hrs), questionnaires provided at 9, 21, 35 and 61 weeks post-randomization and time it takes to sync and use the provided devices (3 hours per timepoint). The total estimated maximum time is 15 hours, for a total of \$150.00.

These payments will be made via a Visa pre-paid card from a rewards platform called Tremendous, which is linked to the Hugo platform. Hugo contracts with Tremendous to manage payments to patients as they are earned. As surveys are completed, the balance will be automatically credited to the patient's Hugo rewards account which is linked to the email address they used to set up their Hugo account. Patients will receive payments when they respond to the study surveys. When these payments are ready, patients will receive an email with instructions on how to redeem their payment. The Visa card will then be sent to their email as a digital ecard from Tremendous. Patients may redeem their payments at any time once they have accrued a balance. Patients will be given the necessary syncable devices to keep as well. Fair market value of the Fitbit Inspire 2 is \$99.95.

Please see the attached Informed Consent in the IRB submission.

## **7.2 Institutional Review Board (IRB) Review**

The protocol will be submitted to the IRB for review and approval. Approval of the protocol must be obtained before initiating any research activity. Any change to the protocol or study team will require an approved IRB amendment before implementation. The IRB will determine whether informed consent and HIPAA authorization are required.

The IRB will conduct continuing review at intervals appropriate to the degree of risk, but not less than once per year.

A study closure report will be submitted to the IRB after all research activities have been completed.

Other study events (e.g. data breaches, protocol deviations) will be submitted per IRB's policies.

## **7.3 Subject Confidentiality**

Subject confidentiality is held in strict trust by the research team. Subject medical record review will be limited to the just the elements needed to complete the study. The RA will also access the patient's full medical record, with read-only access, within the YNHH Epic electronic medical record (EMR) system. These data will not leave the Epic EMR system in any way, and are only being used to verify baseline eligibility. Data access to the YNHH Epic EMR will only be granted after all necessary trainings are complete and sign off is received from the Yale IRB and YNHH medical records department using the Yale New Haven Health System's Research Request for Medical Records Access form.

Each subject will be assigned a unique study number. A master list linking the unique study number to the human subject will be maintained in a secure encrypted folder on a password protected file.

All patient data will be collected, handled, and stored according the most rigorous accepted standards. Staff involved in the study will be appropriately trained to maximize data security and technical systems will meet or exceed requirements imposed by HIPAA. Sensitive information will always be encrypted in transit and at rest.

#### **7.4 Deviations/Unanticipated Problems**

We do not expect protocol deviations. As noted above in section 6.3.5, we will make significant efforts to reduce non-compliance or participant withdrawal through reminders and contact with patients. If the study team becomes aware of an anticipated problem arise, the event will be reported to the IRB by the RA.

#### **7.5 Data Collection**

Age, gender, date of birth and several categories of health information (provider encounters, notes – if available, medication lists, problem lists, family history, allergies, laboratory findings, procedures, immunizations, vital signs, and medical record numbers) will be collected via the Hugo platform. Patients will also be asked to self-report race, ethnicity, weight and co-morbidities/pre-existing conditions, in addition to pre-existing conditions pulled into Hugo from the EHR. We will also be collecting data provided and synced to the Hugo platform from the and Fitbit.

Patient self-reported data collected via Hugo will include insomnia severity using the self-reported ISI scale, and depression using the PHQ-8. These measures will be used to track sleep and depression improvement progress over the 63-week study period. We will also collect data on daytime sleepiness (using the ESS), stress (measured using PSS-10), health-related quality of life (measured using the SF-12) and anxiety (measured GAD-7). Please see section 6.3.5 for the timing of collection. All patient data will be collected, handled, and stored according the most rigorous accepted standards. Staff involved in the study will be appropriately trained to maximize data security and technical systems will meet or exceed requirements imposed by HIPAA. Sensitive information will always be encrypted in transit and at rest.

#### **7.6 Data Quality Assurance**

The Principal Investigator and research team will ensure all trial data are generated, documented, and reported in accordance with the Good Clinical Practice (GCP) guidelines. There will be regular team-wide meetings that will seek to ensure that GCP guidelines are being met. This study is not being conducted to meet regulatory requirements.

#### **7.7 Study Records**

Study records include: regulatory documents, protocols, consent forms, surveys.

#### **7.8 Access to Source**

This study seeks to leverage a combination of EHR and patient-reported outcome data collected using Hugo, as well as patient-generated health data from the Fitbit. These data will be made available to our research team via enrolled patients electing to connect their specific portals within the Hugo platform and share them with our research team. The NESTcc Data Quality

Framework states that to be useful, the data must possess 4 characteristics: high quality; relevant to purpose and context; amendable to the application of appropriate analytic methods; and interpretable using clinical and scientific judgment. First, the data must be high quality, focused on completeness, accuracy, and timeliness. In a recent study published in April 2020 in *npj Digital Medicine*, we demonstrated that the Hugo platform had high levels of completeness and accuracy (all >90%). We also found that the data were available in near real-time, therefore being timely. However, at baseline, these are EHR data and, thus, will be subject to the limitations of EHR data (e.g. these are not designed specifically for research purposes). That said, the clinical outcomes that we seek to ascertain via EHR data are focused on healthcare utilization, which we think should be accurate (e.g. if a patient had an encounter in an Emergency Department). It is likely that some study participants will link data from multiple EHRs, and we will seek to understand clinical utilization using the dates of different encounters.

